10.4. Concomitant Medications and Procedures

All patients will be instructed to take their standard AP medication throughout the study. All medications, including the standard AP medication and over-the-counter therapies (e.g., vitamins, herbal, and nutritional supplements), taken at the time of the Screening Visit (Week -5 Visit) through the Follow-Up Visit will be recorded in the patient's source documentation and documented in the eCRF.

Any concomitant medication deemed necessary for the wellbeing of the patient may be given at the discretion of the Investigator. Use of medications that are prohibited per protocol may lead to patient withdrawal from the study.

A list of allowed and prohibited concomitant medications is shown in [APPENDIX A](#).

11. STUDY ASSESSMENTS

The Schedule of Assessments is presented in [Table 6](#) and should be referenced for details regarding the collection of each assessment at each visit in the respective study periods. Due to the COVID-19 pandemic and the possibility for site closures and/or travel restrictions, clinical laboratory blood draws may be performed by a Home Health Care service provider or by a local laboratory; other safety and efficacy assessments may be performed remotely via phone/audio or video conferencing platforms (with the exception of Facebook).

Study personnel should strive to perform assessments within the visit window as shown in [Table 6](#) with the understanding that not all assessments may be able to be performed. Safety-related assessments must be prioritized. Missed assessments will be recorded in the eCRF with notation that the missed assessment was due to the COVID-19 pandemic. In case of two consecutive missed safety assessments, continued patient participation in the study must be discussed by the Investigator and the Medical Monitor.

11.1. Demographic Characteristics and Medical History

Demographic characteristics (i.e., sex, ethnic origin, date of birth, and calculated body mass index) will be collected and detailed on the eCRF.

At Week -5, the patients must have a confirmed DSM-V diagnosis of schizophrenia for the past 2 years based on patient's history and also confirmed by psychiatric evaluation and MINI International Neuropsychiatric Interview Psychotic Disorders, version 7.0.2 (MINI, Version 7.0.2; see [APPENDIX L](#)).

11.2. Physical Examination

A full physical examination will include an examination of all major organ systems. Brief physical examinations will be symptom-directed.

11.3. Vital Signs

Vital signs will be measured after the patient has been in a supine or semi-supine position for at least 5 minutes and will include blood pressure, pulse rate, respiratory rate, and temperature.

Weight and height will be measured and used to calculate the patient's BMI. Weight and height will be converted as needed to kilograms and centimeters, respectively, prior to statistical analyses.

11.4. Electrocardiogram (ECG)

Twelve-lead electrocardiograms will be performed after the patient has rested in a supine or semi-supine position for at least 5 minutes. Individual parameters including PR, QT, QTcF, QRS, and RR intervals will be collected. Repeat electrocardiograms (if deemed necessary) should be performed at least 5 minutes apart. The Investigator should indicate review of the electrocardiogram reports throughout the study by signing and dating each report.

11.5. Clinical Laboratory Assessments

Clinical laboratory assessments will include serology, hematology, coagulation laboratory parameters, serum chemistry, serum renal laboratory parameters, complete urinalysis, urine pregnancy test, urine drug screen and alcohol breath test. The list of specific tests is shown in [APPENDIX B](#). Samples for laboratory assessments should be collected at the beginning of the Study Visit and prior to the dose.

The results of the laboratory tests conducted at Week -5 must be assessed by the Investigator to determine each patient's eligibility for participation in the study. The Investigator should indicate review of the laboratory reports throughout the study by signing and dating each report.

Where applicable, laboratory results that fall outside the reference range will be interpreted by the Investigator as Abnormal, not clinically significant, or Abnormal, clinically significant. Laboratory results deemed Abnormal, clinically significant will be recorded as an adverse event in the eCRF and should be fully investigated and repeated for verification. Clinically significant laboratory abnormalities requiring intervention should be discussed with the Medical Monitor. Additional tests and evaluations required to establish the significance or etiology of a clinically significant abnormal result or to monitor the course of an adverse event should be obtained when clinically indicated. Whenever possible, the etiology of the clinically significant abnormal findings will be documented on the eCRF.

Any significant laboratory abnormalities that are either serious or unexpected will be promptly reported to the Sponsor. Any additional relevant laboratory results obtained by the Investigator during the course of this study will be reported to the Sponsor or designee.

11.6. Assessment of Efficacy

11.6.1. Positive and Negative Symptom Scale (PANSS)

The PANSS is a psychiatric rating scale designed to measure symptom severity among patients with schizophrenia over the preceding 7 days. The PANSS items are divided into positive, negative and general psychopathology factors utilizing a 30-item, 7-point rating scheme. Scoring instructions will be provided (to the Rater) with each item accompanied by a complete definition as well as detailed anchoring criteria for all 7 rating points, which represent increasing levels of psychopathology: 1=absent, 2=minimal, 3=mild, 4=moderate, 5=moderate severe, 6=severe and 7= extreme. The PANSS is scored by summation of ratings across items such that the potential ranges are 7 to 49 for each of the Positive and Negative Scales and 16 to 112 for the General Psychopathology Scale. The PANSS total score is the score of all 30 PANSS items taken together. (see [APPENDIX C](#))

11.6.2. Clinical Global Impression-Severity (CGI-S) Score

The CGI-S rating scale is a commonly used measure of symptom severity and treatment response. The severity scale (CGI-S) is a 7-point scale that requires the clinician to rate the severity of the patient's illness at the time of assessment. (see [APPENDIX D](#))

11.6.3. Personal and Social Performance Scale (PSP)

The PSP is measure of personal and social functioning of patients with psychiatric disorders. The scale is a hundred-item scale, divided in 10 similar intervals. The score is based on the assessment of a patient's performance in four categories: socially useful activities, personal and social relationships, self-care, disturbing and aggressive behavior. (see [APPENDIX E](#))

11.6.4. Schizophrenia Quality of Life Scale (SQLS)

The SQLS is a self-report Quality of Life scale developed specifically for patients with schizophrenia. It is a 30-item questionnaire comprised of three domains ('psychosocial', 'motivation and energy', and 'symptoms and side-effects'). (see [APPENDIX F](#))

11.7. Extrapyramidal Symptoms

11.7.1. Simpson-Angus Scale (SAS)

The SAS consists of a list of 10 symptoms of parkinsonism (gait, arm dropping, shoulder shaking, elbow rigidity, wrist rigidity, head rotation, glabella tap, tremor, salivation, and akathisia). Each item is rated on a 5-point scale, with a score of one representing absence of symptoms, and a score of 5 representing a severe condition. The SAS total score is the sum of the scores for all 10 items. (see [APPENDIX G](#))

11.7.2. Abnormal Involuntary Movement Scale (AIMS)

The Abnormal Involuntary Movement Scale (AIMS) is a 10-item clinician-rated scale to assess severity of dyskinesias (specifically, orofacial movements and extremity and truncal movements) in patients taking neuroleptic medications. Body areas of interest include Facial and Oral, Extremities and Lower, and Trunk. Each item is scored on an ordinal scale that ranges from 0 to 4: none, minimal, mild, moderate, or severe. Additional global items assess the overall severity, tardive dyskinesia-associated functional impairment, and the patient's level of awareness of the movements and distress associated with them. (see [APPENDIX H](#))

11.7.3. Barnes Akathisia Rating Scale (BARS)

The Barnes Akathisia Rating Scale (BARS) consists of 4 items related to akathisia: objective observation of akathisia by the Investigator, subjective feelings of restlessness by the patient, distress due to akathisia, and global evaluation of akathisia. The first 3 items are rated on a 4-point scale, with a score of 0 representing absence of symptoms and a score of 3 representing a severe condition. The global clinical evaluation is made on a 6-point scale, with 0 representing absence of symptoms and a score of 5 representing severe akathisia. To complete this scale, patients are observed while they were seated and then standing for a minimum of 2 minutes in each position. Symptoms observed in other situations (e.g., while engaged in neutral conversation or engaged in activity on the ward) are also rated. Subjective phenomena are to be elicited by direct questioning. (see [APPENDIX I](#))

11.8. Columbia-Suicide Severity Rating Scale (C-SSRS)

The Columbia Suicide Severity Rating Scale (C-SSRS) is a suicidal ideation rating scale. The scale identifies behaviors and thoughts that are associated with an increased risk of suicidal actions in the future. There are 2 versions of the scale being used in this protocol. (see [APPENDIX J](#))

11.9. Antipsychotic (AP) Medication Blood Level

Blood samples will be taken to assess blood levels of the AP medication being taken by the patient. The confirmation of levels of one of the AP medications listed in [APPENDIX A](#) will be required to be eligible for randomization to the Treatment Period. The details on collection, processing, storage and shipping of blood samples for AP assessment can be found in the study Laboratory Manual.

11.10. CTP-692 Blood Level

CTP-692 blood levels will be measured following study completion. The details on collection, processing, storage and shipping of blood samples for CTP-692 assessment can be found in the study Laboratory Manual.

11.11. Genetic Testing

A blood sample for genetic testing is optional. Only one blood sample is required for genetic testing. The genetic markers analyzed may be related to clinical symptoms, and/or other factors as determined by the Sponsor. The details on collection, processing, storage and shipping of blood samples for genetic testing can be found in the study Laboratory Manual.

11.12. Unscheduled Visit

In addition to regularly scheduled protocol visits, an Unscheduled Visit may be conducted to ensure appropriate safety monitoring or follow-up of the patient, at the discretion of the Investigator. For example, an Unscheduled Visit may be scheduled to monitor potential or actual clinically meaningful safety laboratory results or for other clinical signs, symptoms, or considerations that warrant additional safety follow-up. An Unscheduled Visit may also be conducted to accommodate repeat testing of non-safety related laboratory assessments. Only those criteria requiring additional monitoring should be performed at the Unscheduled Visit. An Unscheduled Visit will not replace regularly scheduled protocol visits.

12. ADVERSE EVENTS

12.1. Definition of Adverse Events

An adverse event (AE) is any untoward medical occurrence that may appear or worsen in a patient during the course of a study. It may be a new intercurrent illness, a worsening concomitant illness, an injury, or any concomitant impairment of the patient's health, including laboratory test values, regardless of etiology. Any worsening (i.e., any clinically significant adverse change in the frequency or intensity of a pre-existing condition) should be considered an adverse event. A diagnosis or syndrome should be recorded on the adverse event page of the eCRF rather than the individual signs or symptoms of the diagnosis or syndrome. A worsening of the condition under study will not be reported as an adverse event.

All patients will be monitored for adverse events during the study. Assessments may include monitoring of the following parameters: the patient's clinical symptoms, laboratory, physical examination findings, or findings from other tests and/or procedures.

An adverse event reported after informed consent, but before the first dose of Study Medication (i.e., Day 1), will be considered a pretreatment adverse event and will be captured on the eCRF. Adverse events will be considered treatment-emergent if the onset is after the first dose of Study Medication.

An abnormal laboratory value is considered to be an adverse event if the abnormality:

- results in discontinuation from the study;
- is judged by the Investigator to be of significant clinical importance requiring treatment, modification/interruption of investigational product dose, or any other therapeutic intervention.

Regardless of severity grade, only laboratory abnormalities that fulfill a seriousness criterion need to be documented as a serious adverse event.

If a laboratory abnormality is one component of a diagnosis or syndrome, then only the diagnosis or syndrome should be recorded on the adverse event eCRF. If the abnormality was not a part of a diagnosis or syndrome, then the laboratory abnormality should be recorded as the adverse event. If possible, the laboratory abnormality should be recorded as a medical term and not simply as an abnormal laboratory result (e.g., record thrombocytopenia rather than decreased platelets).

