12.2.1. Serious Adverse Event (SAE)

A serious adverse event is an adverse event, as per Title 21 CFR 312.32 and ICH E2A.II.B that fulfills the following criteria:

- Is fatal (results in death);
- Is life-threatening (Note: the term "life-threatening" refers to an event in which the patient was at risk of death at the time of the event; it does not refer to an event that could hypothetically have caused death had it been more severe);
- Requires inpatient hospitalization or prolongation of existing hospitalization (hospitalization is defined as an inpatient admission, regardless of length of stay);
- Results in persistent or significant disability/incapacity (a substantial disruption of the patient's ability to conduct normal life functions);
- Is a congenital anomaly/birth defect; or
- Constitutes an important medical event that may jeopardize the patient or may require medical or surgical intervention to prevent one of the other outcomes listed above.

Important medical events are defined as those occurrences that may not be immediately life-threatening or result in death, hospitalization, or disability, but may jeopardize the patient or require medical or surgical intervention to prevent one of the other outcomes listed above. Examples of such medical events include allergic bronchospasm requiring intensive treatment in an emergency room or at home, blood dyscrasias or convulsions that do not result in inpatient hospitalization.

Events **not considered** to be serious adverse events are hospitalizations for:

- A procedure for protocol/disease-related investigations (e.g., sampling for laboratory tests). However, hospitalization or prolonged hospitalization for a complication of such procedures remains a reportable serious adverse event.
- Hospitalization or prolongation of hospitalization for technical, practical, or social reasons, in absence of an adverse event.
- A procedure that is planned (i.e., planned prior to the starting of treatment on study); must be documented in the source document and the eCRF. Hospitalization or prolonged hospitalization for a complication remains a reportable serious adverse event.
- An elective treatment of or an elective procedure for a pre-existing medical condition that does not worsen.
- Emergency outpatient treatment or observation that does not result in admission, unless fulfilling other seriousness criteria above.

If an adverse event is considered serious, the adverse event eCRF must be completed.

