12.3.8. Reporting Serious Adverse Events

The Investigator is required to notify the Sponsor, and the Sponsor's designated Drug Safety Unit within 24 hours after becoming aware of the occurrence of a serious adverse event. All serious adverse events will be reported through completion of the adverse event eCRF. The Investigator will be responsible for reporting serious adverse events to the IRB.

Emergency Contact Information:

Dr. [REDACTED]

[REDACTED]
e-mail: [REDACTED]
Fax: [REDACTED]

Phone: [REDACTED]

e-mail: [REDACTED]

If an Investigator becomes aware of a serious adverse event within 4 weeks after the last dose of Study Medication and it is considered by him/her to be caused by the Study Medication with a reasonable possibility, the event must be documented and reported through completion of the adverse event eCRF.

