### 4.5.1 Adverse Events

An adverse event (AE) is any untoward medical occurrence that may appear or worsen in a patient during the course of a study. It may be a new intercurrent illness, a worsening concomitant illness, an injury, or any concomitant impairment of the patient's health, including laboratory test values, regardless of etiology. Any worsening (i.e., any clinically significant adverse change in the frequency or intensity of a pre-existing condition) will be considered an adverse event.

A worsening of the condition under study will not be considered as an AE.

An AE can be any unfavorable and unintended sign (including a new, clinically important abnormal laboratory finding), symptom, or disease temporally associated with the Study Medication, whether or not it is related to the product.

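### Read literally, the plan leaves a psychotic exacerbation that leads to hospital admission out of SAE reporting and out of the by-arm SAE tables

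*Protocol*

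**What the plan says.** Protocol 12.1 first gives a general rule that worsening counts: "any clinically significant adverse change in the frequency or intensity of a pre-existing condition) should be considered an adverse event". Later in the same paragraph it makes an exception for the disease being treated: "A worsening of the condition under study will not be reported as an adverse event". SAP 4.5.1 follows it: "A worsening of the condition under study will not be considered as an AE". Neither sentence carries a qualifier about seriousness.

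Protocol 12.2.1 builds the SAE on the AE: "A serious adverse event is an adverse event, as per Title 21 CFR 312.32". One of its seriousness criteria is "Requires inpatient hospitalization or prolongation of existing hospitalization (hospitalization is defined as an inpatient admission, regardless of length of stay". The section then lists hospitalisations that do not count as SAEs. Exacerbation of schizophrenia is not among them; the nearest item is "An elective treatment of or an elective procedure for a pre-existing medical condition that does not worsen".

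Protocol 12.3.8 requires the sponsor and its drug safety unit to be told of an SAE within 24 hours and names the form: "All serious adverse events will be reported through completion of the adverse event eCRF".

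Protocol 13.4.5 and SAP 5.5.1 tabulate treatment-emergent AEs by arm, and SAEs as a subset of them.

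**The concern.** The exclusion has an understandable purpose. Symptom severity is the efficacy outcome, and recording every fluctuation as an AE would duplicate PANSS and CGI-S. The wording goes further than that purpose needs, because it removes serious worsening along with ordinary symptom change.

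Admission for psychosis is a foreseeable serious event in outpatients with schizophrenia. Safety is a stated objective, Protocol 7.4 sets no prospective stopping criteria, and SAP 5.7 plans no interim analysis, so SAE reporting carries much of the oversight while the trial runs. At stake are that notification route and a count, by arm, of serious exacerbations on three doses of CTP-692 and placebo.

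**Working it through.** The plan states no figure on this point, so the check is mainly a reading of the definitions in sequence.

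**The chain**

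1. A patient has a psychotic exacerbation and is admitted. Under the general rule in Protocol 12.1 this is an AE. Under the exclusion in the same section, and in SAP 4.5.1, it is not. The exclusion is the more specific sentence and is unqualified, so it is best read as a carve-out that prevails.
2. The admission meets a seriousness criterion in 12.2.1 and is not on the exempt list. That section applies its criteria only to adverse events, so an event removed at step 1 never reaches them.
3. The 24-hour notification and the AE eCRF in 12.3.8 apply to SAEs, so they are not triggered.
4. The by-arm SAE tables in Protocol 13.4.5 and SAP 5.5.1 are subsets of the treatment-emergent AE summaries. The event is not in their source data.

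Protocol 12.1 does apply a seriousness test elsewhere: "only laboratory abnormalities that fulfill a seriousness criterion need to be documented as a serious adverse event". It sets no matching threshold for worsening of schizophrenia.

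**What other outputs would capture**

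| Source | Captures | Does not give |
|---|---|---|
| Disposition by reason, by arm (SAP 5.3) | Exacerbations ending in withdrawal, if the reason is recorded that way | Patients admitted who stay in |
| Concomitant antipsychotic table (SAP 5.5.10) | Added or changed antipsychotics | A count of events; all patients take a background antipsychotic |
| PANSS (Protocol 11.6.1) | Symptoms over the preceding 7 days at Weeks 2, 4, 8, 10 and 12 | Admissions; between Weeks 4 and 8, 28 − 7 = 21 days lie outside recall |
| CGI-S (Protocol 11.6.2) | Severity at each clinic visit from Week 2 to Week 12 | Events between visits |
| C-SSRS (SAP 5.5.2) | Suicidal ideation and behaviour | Psychosis without suicidality |
| Urgent safety issues and IRB notice (Protocol 12.3.9, 14.3) | Individual cases | Any table |

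A fatal event would still appear in the listing of deaths in SAP 5.5.1.

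**How likely the rule is to be used**

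The documents give no exacerbation rate, so the values of p below are assumptions. With 300 patients (Protocol 7.3) and a 12-week rate p, the chance of at least one such event is 1 − (1 − p)^300:

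- p = 0.1%: 1 − 0.999^300 = 0.26
- p = 0.23%: 0.50, from p = 1 − 0.5^(1/300)
- p = 0.5%: 1 − 0.995^300 = 0.78
- p = 1%: 1 − 0.99^300 = 0.95

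At 1% the expected number per arm is 75 × 0.01 = 0.75. The calculation shows how readily the rule could come into play. It does not show that any by-arm comparison would change.

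**The case against.** The strongest reply is that the rule is deliberate: protocol and SAP agree, schizophrenia severity is already the efficacy outcome, and the trial analyses it by arm and visit. Events may also be few, because Inclusion Criterion 4 excludes anyone hospitalised for worsening in the 3 months before screening. All of this stands as a reason to keep non-serious symptom change out of the AE tables. It does not explain leaving out worsening that 12.2.1 would otherwise call serious.

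A second reply is that the text pulls both ways. The general worsening rule and the list of exempt hospitalisations could lead a site to report an admission as an SAE anyway. That is possible, and it is why the point is put as a literal reading. It supports reconciling the sections rather than leaving them alone.

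A third reply limits the point. A reader might infer that exacerbations would be invisible by arm. The documents do not support that: those ending in withdrawal can appear in disposition by reason, and others can show indirectly in the outputs tabulated above. A reader might also compare the plan unfavourably with the D-serine experience in Protocol 4.1, where psychosis is reported by arm. That figure is a count of withdrawals, an output type SAP 5.3 already plans, in people at clinical high risk. The comparison does not help. Nor would a zero in the SAE table necessarily mislead, since SAP 4.5.1 says openly that worsening is not an AE.

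Finally, SAP section 7 leaves the table list to a separate document, so a further table could be added. It would need a data source, and neither document describes a form that records psychiatric admissions outside AE reporting.

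**Conclusion.** The concern holds as a gap in safety reporting. Followed literally, the plan leaves a hospitalised exacerbation unreported as an SAE and absent from the SAE tables. The loss is the SAE notification and a by-arm count of serious exacerbations, clearest for a patient who is admitted and continues in the study.

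Its size cannot be estimated from the documents. The verdict assumes that the specific exclusion prevails over the general worsening rule and that no eCRF instruction outside these documents restores serious events. A reader might infer that the efficacy result is compromised. It is not: the definition of an AE does not enter the primary endpoint, its model or the power calculation. The point is worth fixing because the remedy is cheap and directly improves safety reporting.

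**What to change.** Reconcile Protocol 12.1, 12.2.1 and 12.3.8 with SAP 4.5.1 so that the exclusion covers only non-serious symptom change already measured by PANSS and CGI-S. State that worsening of schizophrenia meeting a seriousness criterion is reported as an SAE and included in the existing by-arm SAE tables.

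The same amendment must address Protocol 9.3, under which a patient with a serious AE should be withdrawn. The sponsor should state whether an exacerbation reported under the new text triggers that criterion; no withdrawal rule is proposed here.

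The cost is a qualified sentence in 12.1, consistent wording in the linked sections, eCRF guidance and matching SAP text, plus some extra SAE processing. No new table is needed. The main risk lies in leaving 9.3 unreconciled. Affected patients would then meet a withdrawal criterion, and under SAP 5.1.5 their Early Termination PANSS goes to the window matching its date. The Week 12 window opens at Day 78, so an earlier withdrawal would leave Week 12 PANSS missing and dependent on the missing-at-random assumption in SAP 5.1.4. The defect itself does not touch the primary endpoint, but a careless fix could.
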